7.7 Data Analysis

Prior to conducting the data analyses, we will perform data management (as described in section 7.6) to ensure data quality and to correct inconsistencies and errors in the data. The data analysis will include the following five steps listed below. Note that specifications concerning all pre-defined supplementary analyses will be detailed in a separate statistical analysis plan before database lock and start of data analysis. The assumptions of the statistical models performed will be evaluated for each model in the analysis.

7.7.1 Substudy 1: Descriptive analysis of exposure of DL

A cohort study describing DL use in the general population will be performed. A person with prescription redemption of DL in Norway and Sweden within the first 6 months after establishment of the prescriptions registers will not be included in order to avoid left-truncation bias. In addition, to avoid analogous misclassification of prevalent with incident DL dispensings among immigrants, we exclude persons with DL prescription redemptions within 6 months after immigrating to Denmark, Finland, Norway, or Sweden. Prevalent users will be defined as persons who have at least one prescription of DL in the period of interest (e.g., the entire study period or each year). Incident users are first time users of DL in the period of interest. The following descriptive analyses will be performed:

- The distribution of prevalent and incident users in the total population and stratified by country, age, sex, calendar year, seasonality, severity of rhinitis, asthmatic status, and chronic urticaria status.
- Descriptive information on the mean, standard deviation, median, and maximum and minimum number of redeemed DL prescriptions in the total population and stratified by country, age, sex, calendar year, seasonality, severity of rhinitis, asthmatic status, and chronic urticaria status.

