The cohort of individuals with redeemed DL prescriptions will be identified from the four Nordic national prescription registers. Similarly, the cohort of all individuals with seizures (first seizure), the cohort of individuals with SVT, and the cohort of individuals with A-fib/flu will be identified from the four Nordic national patient registers. The population is comprised of all individuals with DL prescriptions and of all individuals with seizures, SVT, or A-fib/flu in the four Nordic countries in the period 2001–2015 in Denmark and Finland, 2008–2015 in Norway, and July 2005–2015 in Sweden (Table 5). Individuals for Substudies 2B, 3B, and 4B become eligible for the study cohort upon first dispensing of DL (See sections 7.2.1 and 7.2.2). Data will be available until and including 2015 for all countries.

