- Left-truncation is a potential bias in the study meaning that we have no information on DL use before the start of registration of prescriptions in each country. Left-truncation bias in relation to DL use is only a relevant issue for Sweden and Norway since DL was available from 2001, but the prescription registers in Norway and Sweden were established in 2004 and 2005, respectively (Table 4). Therefore, we do not know whether a DL user in the first year of registration in Norway and Sweden is a long-term user (prevalent user) or a first-time user (incident user). To account for this potential bias, a person with prescription redemption of DL in Norway and Sweden within the first 6 months after establishment of the prescriptions registers will not be included. This is not a limitation in Denmark and Finland since DL was first approved in 2001 and the prescription registers in Denmark and Finland were established in 1995 and 1994, respectively. However, left-truncation bias might also occur when persons are immigrating into the study population. Therefore we also exclude persons with DL prescription redemptions within 6 months after immigrating to Denmark, Finland, Norway, or Sweden.
- There is a possibility that patients could purchase DL over-the-counter; however, because of reimbursement systems in the Nordic countries, it is actually less expensive to purchase prescription DL. In Norway and Sweden DL has only been allowed for prescription sale; However, in Denmark, DL has been available for over-the-counter sale since 2013, but over-the-counter sales only counted for less than 4 % of the total amount of DL purchased in 2013. A supplementary analysis will examine the associations under consideration restricting the time period to include only years where DL was not allowed for OTC sale.
- Loratadine, the parent compound of DL, is also available via prescription and over-the counter in the Nordic countries. We think it is somewhat unlikely that patients would switch between DL and loratadine. However, it is possible that some of the time counted as unexposed in the analyses could actually be time exposed to loratadine or over-the-counter DL. Moreover, other non-sedating prescription antihistamines are available in the Nordic countries, and if the effect on the outcomes

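### Section 7.7.1 applies two new-user washouts to the whole of Substudy 1, so people who are prevalent users by the protocol's own definition drop out of the utilisation figures

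*Protocol*

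**What the plan says.** Section 7.7.1 opens Substudy 1 with a person-level exclusion: someone in Norway or Sweden with a DL redemption "within the first 6 months after establishment of the prescriptions registers will not be included in order to avoid left-truncation bias". The next sentence extends the idea to people who redeem DL within 6 months of immigrating to any of the four countries.

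Only then are the two user types defined:
- "Prevalent users will be defined as persons who have at least one prescription of DL in the period of interest", where the period may be the whole study or a single year.
- "Incident users are first time users of DL in the period of interest".

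The first planned output is "The distribution of prevalent and incident users in the total population and stratified by country, age, sex, calendar year" and further factors. The second is the mean, standard deviation, median, minimum and maximum number of redeemed prescriptions over the same strata. Nothing limits either exclusion to incident users or to one of the outputs.

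Section 7.9 gives the reason. For the start of registration in Norway and Sweden it is not known whether a DL user "is a long-term user (prevalent user) or a first-time user (incident user"). It dates the registers by year only: "the prescription registers in Norway and Sweden were established in 2004 and 2005, respectively". Section 7.2 sets the study periods as "2008–2015 in Norway, and July 2005–2015 in Sweden".

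**The concern.** A washout protects the label of new user. Someone seen early in a register may have started before it existed, so calling that person incident would be wrong. Prevalent use, as section 7.7.1 defines it, needs no history: one redemption in the period is enough. Removing the person from prevalent counts corrects no error and loses a true user.

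Describing DL use by country, calendar year and other factors is the first primary objective in section 6. The exclusion is permanent for the person, so it reaches every later year and fades only as new users enter. The register-start rule touches two of the four countries, which affects country comparisons. The immigration rule touches all four. Section 7.2.1 also brings the general population on 1 January of each year into Substudy 1 without any matching exclusion, so users leave the numerator while the population they are set against stays whole.

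**Working it through.** The protocol gives no user counts by country and year and no figure to reproduce on this point. The check therefore compares the text, works through the calendar, and illustrates who is caught.

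**1. Text side by side**
- Section 7.2.1, Substudy 1: everyone resident in the four countries with at least one DL redemption in the study period is included.
- Section 7.2.2: the list starts at Substudy 2A and contains no Substudy 1 exclusion.
- Section 7.1, Substudy 1: both prevalent and incident users are to be identified and described.
- Section 7.7.1: some of those same people are not included at all.

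The last item cannot be carried out together with the first.

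**2. Sweden, calendar arithmetic**
Swedish study time in 2005 runs from 1 July to 31 December, 184 days. The window is the register start plus 6 months. The start month is not stated, so it is varied:

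| Assumed register start | Window ends | 2005 study days outside the window |
|---|---|---|
| 1 January 2005 | 1 July 2005 | 184 of 184 |
| 1 April 2005 | 1 October 2005 | 92 of 184 |
| 1 June 2005 | 1 December 2005 | 31 of 184 |
| 1 July 2005 | 1 January 2006 | 0 of 184 |

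With a July start, every 2005 redeemer is excluded and the Swedish 2005 cell is empty by construction. With a January start, no study day falls in the window, although people who redeemed between January and June 2005 would still be missing from later years.

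**3. Norway**
A register established at some point in 2004 puts the end of the window between July 2004 and mid-2005. The study period starts in 2008, at least 2.5 years later, so no study year is emptied. People who redeemed in the window and still use DL in 2008–2015 are lost, provided the 2004 prescription data are used. Table 5 lists the Norwegian prescription register from 2004 but a data extraction period of 2008–2015, so this is conditional.

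**4. Who is caught (illustration, by assumption)**
For a person already using DL during the window at a constant rate of r prescriptions per year, with Poisson redemptions, the chance of at least one redemption in half a year is 1 − exp(−r/2):
- r = 0.5: 0.221
- r = 1: 0.393
- r = 1.50, 1.62, 1.78, 2.30 (the age-group means in section 7.5.2): 0.528, 0.555, 0.589, 0.683
- r = 4: 0.865

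Tables 6–8 pair those means with people who have at least one prescription a year, so a zero-truncated Poisson fits them better. Solve λ/(1 − exp(−λ)) = mean, then compute (1 − exp(−λ/2))/(1 − exp(−λ)). For the four age groups, λ = 0.874, 1.057, 1.290 and 1.984, giving 0.608, 0.629, 0.656 and 0.729.

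The chance of removal rises with frequency of use, but the contrast across the protocol's own means is modest. For anyone who started after the window it is 0.

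**The case against.** The other side has several fair points.

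- **Consistency with the association analyses.** Substudies 2B, 3B and 4B use the same two exclusions, so Substudy 1 as written describes the cohort that is analysed. Section 7.2.2 omits the washouts for those substudies too, so its silence on Substudy 1 may be an editorial habit. This stands as an explanation. It does not serve an objective framed as use in the general population, and the conflict with 7.2.1 remains.
- **Continuity with the earlier study.** Section 5 says the only change from the earlier protocol is the removal of secondary analyses, and that the report will build on the three-country report. Changed Substudy 1 figures would no longer match it. This is a real cost, and showing both versions meets it.
- **Limited reach.** Substudy 1 is descriptive and no rate ratio depends on it. Even on the July reading, the empty Swedish cell is about 0.5 of 10.5 study years (5%), and its cause is disclosed. This bears on how serious the point is, not on whether it is right.

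Three stronger readings are tempting but unsupported:
- A reader might infer that Sweden must show no users in 2005. That needs a July 2005 register start. The July date in section 7.2 belongs to the study period, and a January register start followed by a 6-month washout would also give it.
- A reader might infer that frequent users as a class are removed for good. A single redemption in the window removes anyone, and frequent users who start later stay in.
- A reader might take the percentages above as the size of the bias. They apply only to people active in the window. Section 5 reports Danish annual users rising from 7,317 in 2001 to 51,564 in 2012. If Norway and Sweden were similar, which is an assumption, many later users started after the window.

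**Conclusion.** The point holds for the text of section 7.7.1. Two washouts that are justified only for incident use are applied to whole persons across Substudy 1, against section 7.2.1. The direction for prevalence is clear: it is understated. Prescriptions per user, time trends and country comparisons are distorted. If redemptions behave roughly as in the illustration, frequent users active in the window are more likely to be lost, which would tend to lower prescriptions per user in Norway and Sweden.

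The size cannot be computed from the protocol. It depends on the Swedish register start month, on whether the 2004 Norwegian prescription data are used, and on how many early redeemers or recently immigrated redeemers were still using DL later. The protocol gives none of these. The change should be made because it affects a primary objective, but it does not bear on the safety comparisons.

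**What to change.** - In section 7.7.1, apply the register-start and post-immigration exclusions only when classifying incident users.
- Keep everyone with a redemption in the study period in the prevalent-user counts and the prescriptions-per-user tables.
- State the start date of the Swedish prescription register and whether Norwegian prescription data before 2008 will be used.
- Align sections 7.2.1, 7.2.2 and 7.7.1 so that the Substudy 1 population is described once and in the same way.
- Report the tables with the exclusions alongside, so that the figures can be compared with the earlier three-country report.

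The cost is a short text change, one filter in the programming and a second set of descriptive tables. The main downside is that the new headline figures will differ from those already reported for Sweden and, through the immigration rule, for Denmark and Finland. The side-by-side tables explain that difference.

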7.7.2 Substudy 2: First seizure

Substudy 2A

A cohort study estimating the incidence of first seizures in the general population will be conducted. The cohort of individuals with seizures and the distribution of the population by age, year, and country will be used to derive estimates for the general population. The number of individuals in the general population on 01 January of each year will be obtained from the NORDCAN database and used as an estimate of the number of person years at risk assuming each person in the population on 01 January of each year contributes one person year at risk [Association of Nordic Cancer Registries 2009]. The IRs of seizure will be shown for the total population and stratified by country, sex, and age. The 95% confidence interval for IRs will be calculated as:

$$\dots / \exp(1.96/\sqrt{N_{new\ users}}) \text{ to } IR * \exp(1.96/\sqrt{N_{new\ users}})$$

where IR is the incidence rate, exp is the exponential function, and $N_{new\ users}$ is the number of new users [Kirkwood, B. R. 2003].

Substudy 2B

A cohort study among ever-DL users analyzing the association between exposed and unexposed time and first seizures will be performed for the total population and stratified by age. Current use (i.e., “exposed” period) will be defined for each prescription as days’ supply plus a 4 week grace period to account for intermittent use and a possible wash-out effect. Unexposed time will be defined as the period starting 26 weeks from the dispensing date of the prior DL prescription until the next DL prescription redemption, if any. A person who has redeemed at least one prescription of DL is included in the cohort and enters the cohort at the date of first prescription redemption. Study individuals are followed until occurrence of a seizure; occurrence of one of the conditions described in section 7.2.2; 31 December 2015; emigration; or death, whichever comes first. The association between exposure to DL and first seizure will be evaluated using Poisson regression of the IR of first seizure, and the measure of effect is the IRR. A person with prescription redemption of DL in Norway and Sweden within the first 6 months after establishment of the prescriptions registers will not be included in order to account for truncation bias. In addition we exclude persons with DL prescription redemptions within 6 months after immigrating to Denmark, Finland, Norway, or Sweden. The analyses will be adjusted for confounders identified from the DAG (i.e., country, age, sex, calendar year, seasonality, severity of rhinitis, asthmatic status, and chronic urticaria status) (Table 4). We will evaluate whether age can be included as a continuous variable by examining the assumption of linearity. Alternatively, age will be included as a categorical variable.

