DL is a prescription oral antihistamine approved in the European Union (EU) for the relief of symptoms associated with allergic rhinitis and urticaria in both adults and children (Annex 5. Data from the Danish National Prescription Register (www.medstat.dk/en; accessed 28 May 2014) suggest that about 270,000 Danish citizens (about 5% of the population) purchase antihistamines with a prescription at least once annually. This figure has been rather stable since the year 2000. The number of Danish citizens who purchase DL by a prescription at least once annually has increased from 7,317 in 2001 to 51,564 in 2012. The number of Danish children aged 0–4 years who purchased DL with a prescription at least once annually has increased from 8 in 2001 to 6,815 in 2012. The number of Danish children aged 5–19 years who purchased DL with a prescription at least once annually has increased from 935 in 2001 to 11,447 in 2012. In 2012, children aged 0–4 years accounted for 37% of all children (0–19 years) who purchased DL at least once. The background incidence of unprovoked seizures is rare; approximately 0.4-0.6 per 1,000 population per year [Hauser, W. A. and Beghi, E. 2008]. Patients with epilepsy experience seizures; however, not all individuals with seizures have epilepsy and not all seizures evolve into epilepsy [Hauser, W. A. and Beghi, E.

2008]. A previous study described clinical observations of seizures induced by DL in four children [Cerminara, C., et al 2013].

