7.7.3 Substudy 3: SVT

Substudy 3A

A cohort study estimating the incidence of SVT in the general population will be performed. The cohort of DL users, the cohort of individuals with SVT, and the distribution of the population by age, year, and country will be used to derive estimates in the general population. The number of individuals in the general population on 01 January of each year will be obtained from the NORDCAN database and used as an estimate of the number of person years at risk assuming each person in the population on 01 January of each year contributes one person year at risk [Association of Nordic Cancer Registries 2009]. The IRs of SVT will be shown for the total population and stratified by country, sex, and age. The confidence interval of IRs is calculated as outlined above under Substudy 2A.

Substudy 3B

A cohort study among ever-DL users analyzing the association between exposed and unexposed time (as defined in Substudy 2B) and first SVT will be performed for the total population and stratified by age. A person who has redeemed at least one prescription of DL is included in the cohort and enters the cohort at the date of first prescription redemption. Study individuals are followed until occurrence of a SVT; 31 December 2015; emigration; or death, whichever comes first. The association between exposure to DL use and first SVT will be evaluated using Poisson regression of the IR of first SVT, and the measure of effect is the IRR. A person with prescription redemption of DL in Norway and Sweden within the first 6 months after establishment of the prescriptions registers will not be included in order to account for truncation bias. In addition we exclude persons with DL prescription redemptions within 6 months after immigrating to Denmark, Finland, Norway, or Sweden. The analyses will be adjusted for confounders identified from the DAG (i.e., country, age, sex, calendar year, seasonality, severity of rhinitis, asthmatic status, and chronic urticaria status) (Table 4). We will evaluate whether age can be included as a continuous variable by examining the assumption of linearity. Alternatively, age will be included as a categorical variable.

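### The 95% confidence interval for the general-population incidence rates (Substudies 2A, 3A and 4A) is built on the number of new drug users when it should use the number of incident cases

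*Protocol*

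**What the plan says.** Protocol section 7.7.2 describes Substudy 2A as follows: "A cohort study estimating the incidence of first seizures in the general population will be conducted". Person-time is the 1 January population, "assuming each person in the population on 01 January of each year contributes one person year at risk". The rates are to be shown overall and by country, sex and age. For precision, the section states: "The 95% confidence interval for IRs will be calculated as", followed by an error-factor formula in which the rate is divided and multiplied by exp(1.96/√N). The N carries the subscript for new users in the formula, and the sentence below it says that N "is the number of new users".

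Section 7.7.3 carries this into Substudy 3A: "The confidence interval of IRs is calculated as outlined above under Substudy 2A". Section 7.7.4 does the same for Substudy 4A.

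Section 7.7 describes new users in one other place, under Substudy 1: "Incident users are first time users of DL in the period of interest".

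**The concern.** The error-factor form is a standard Poisson interval for a rate, provided that the count under the square root is the number of events in the numerator. Here the events are first seizures, first SVT or first A-fib/flu diagnoses in the whole population. People starting DL are a different group, and their number carries no information about the precision of these rates.

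Describing the three rates is among the primary objectives in section 6. If the formula is programmed as printed, the error bars on those rates will reflect how widely DL was taken up in a stratum and will not respond to how many cases occurred there. A reader comparing countries, sexes or age groups could take chance differences for real ones, or miss real ones.

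**Working it through.** The protocol prints a formula but no numerical interval, so there is no figure to reproduce. The check is of the formula itself.

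**Correct form.** For d cases over fixed person-time, Var(log IR) ≈ 1/d. The 95% limits are therefore IR/exp(1.96/√d) and IR × exp(1.96/√d).

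**Effect of using N new users.** The written interval is √(N/d) times too narrow on the log scale, or too wide if N < d. Its actual coverage is 2Φ(1.96 × √(d/N)) − 1. It is right only where N happens to equal d.

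**Inputs for a one-year Danish illustration, all from section 5:**
- Population: 270,000 antihistamine purchasers are about 5% of Danes, so 270,000/0.05 = 5.4 million.
- Seizure rate: "approximately 0.4-0.6 per 1,000 population per year".
- New DL users: not given. Annual DL users were 7,317 in 2001 and 51,564 in 2012. New users in a year cannot exceed users in that year, so each figure is an upper bound for its own year. They are used here as an assumed range.

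**Cases.** 5.4 million × 0.0004 = 2,160; 5.4 million × 0.0006 = 3,240.

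**Error factors.**

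| Count under the root | Value | exp(1.96/√count) |
|---|---|---|
| Cases, low | 2,160 | 1.043 |
| Cases, high | 3,240 | 1.035 |
| New users, low (assumed) | 7,317 | 1.023 |
| New users, high (assumed) | 51,564 | 1.009 |

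**Extremes of the range.**
- 3,240 cases with 7,317 users: √(7,317/3,240) = 1.5 times too narrow, coverage about 81%.
- 2,160 cases with 51,564 users: √(51,564/2,160) = 4.9 times too narrow, coverage about 31%.

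A Poisson simulation of 200,000 draws with 2,160 expected cases gave 30.8% coverage with 51,564 users under the root and 95.1% with the case count.

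**Opposite direction.** If cases outnumber new users, the interval is too wide. With an assumed 17,000 A-fib/flu cases and 7,317 new users, the written factor is 1.023 and the correct one 1.015. Table 8 shows where this could happen. At 2,154.3 per 100,000 for ages 65 and over, annual cases exceed even all 44,500 annual users in that age group once the population passes 44,500/0.021543 ≈ 2.07 million. The documents do not give that population.

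**Mechanism.** Section 5 reports 8 Danish DL purchasers aged 0–4 in 2001 and 6,815 in 2012. Taken as upper bounds on new users, they give error factors of at least exp(1.96/√8) = 2.0 and exp(1.96/√6,815) = 1.024, whatever the number of seizures in those children. The rates are not planned by calendar year, so this shows only what drives the width.

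**The case against.** The best defence is that this is a labelling slip. The form is correct if N is read as new cases, the wording looks carried over from a calculation of drug-use incidence, and a programmer might use cases anyway. The text also does not say new DL users in so many words. That account of the origin is plausible, but it is inference. The wrong count appears in both the formula and its definition, and no other passage corrects it. The separate analysis plan is no answer either, because the protocol itself fixes the quantity. The independent double programming in section 7.8 would not expose the error if both programmers followed the printed definition.

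Three limits do stand:
- 2A, 3A and 4A are descriptive, and no test between strata is planned for them. Section 6 lists describing the rates as an objective but does not mention intervals.
- For a whole-country rate the absolute gap is modest: about ±4% is correct, against about ±1% to ±2% as written.
- The direction is not uniform.

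A reader might infer more than the documents support. One step would be to insert the 20,000 or 86,000 from section 7.5.1 as new users, set them against a small case count, and conclude that intervals are an order of magnitude too narrow. Those figures are annual unique users, not first-time users, and the protocol gives no case counts by stratum. Another would be to say that all these intervals are too narrow, which fails wherever cases exceed new users. A third would be to doubt the drug–outcome results. The rate ratios in 2B, 3B and 4B come from Poisson regression and do not use this formula.

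**Conclusion.** The interval is wrong as written in Substudy 2A and, by cross-reference, in 3A and 4A. Its width depends on DL uptake and not on case counts, and it is correct only where the two counts coincide.

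In the Danish one-year seizure illustration, it is 1.5 to 4.9 times too narrow on the log scale, with coverage of about 81% down to 31% in place of 95%. This rests on the section 5 seizure rate, a population derived from a rounded 5%, and the assumption that new users lie between 7,317 and 51,564. A smaller number of new users would shrink the discrepancy, and below the case count it would reverse. The size in the planned strata cannot be computed from the protocol, which gives neither new-user nor case counts for them.

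Point estimates of the rates and the rate ratios for the three hypotheses are not affected.

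**What to change.** In section 7.7.2, replace the number of new users by d, the number of incident cases of the outcome in the stratum, and define it so: IR/exp(1.96/√d) to IR × exp(1.96/√d). Name the outcome explicitly in sections 7.7.3 and 7.7.4 (first SVT, first A-fib/flu) so that the cross-reference cannot carry the wrong count forward. Exact Poisson limits where d is small are an optional refinement and are not needed to correct the error.

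The cost is one definition and one program line, with no new data.

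Section 5 says that the methods are unchanged from the three-country protocol apart from dropping the secondary analyses, and that this report will build on the earlier one. The sponsor should therefore also check which count was used for the intervals in the three-country report before the two sets of results are combined.
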